7.3.4 Decision-Change Rates

Statistical Method: Series of exact binomial tests to evaluate decision changes and their clinical impact in Condition Y1 (AI-generated predictions shown after participants recorded their initial diagnoses).

Rationale:

- **Distribution-free:** Does not assume normality or large-sample approximations
- **Appropriate for binary outcomes:** Tests proportions of categorical outcomes (changed/unchanged, beneficial/harmful)
- **Exact inference:** Provides exact p-values based on the binomial distribution rather than asymptotic approximations
- **Multiple hypotheses:** Evaluates whether (1) changes occur, (2) changes are beneficial, and (3) overall improvement is achieved

Analysis Procedure:

1. For Condition Y1 only, identify the diagnosis before (Y1_PRE) and after the AI-generated prediction is displayed (Y1_POST).
2. Calculate overall decision-change rate: proportion of all Y1 cases with diagnostic revision.
3. Classify each decision change according to alignment with ground truth:
 - Beneficial (I→C): Incorrect initial diagnosis corrected after viewing AI
 - Harmful (C→I): Correct initial diagnosis changed to incorrect after viewing AI
4. Statistical Testing:
 - Test 1 - Overall Change Rate:
 1. Null hypothesis: Decision change rate = 0 (no changes occur)
 2. Test: One-sided exact binomial test
 3. Evaluates: Whether clinicians revise their diagnoses after viewing AI
 - Test 2 - Direction of Changes (among changes only):
 1. Null hypothesis: The likelihood of beneficial changes = The likelihood of harmful changes
 2. Test: One-sided exact binomial test comparing number of beneficial vs. harmful changes
 3. Evaluates: Whether changes tend to improve or worsen diagnostic accuracy
 - Test 3 - Overall Improvement Rate (all Y1 cases):
 1. Null hypothesis: Improvement rate = 0 (AI provides no benefit)
 2. Test: One-sided exact binomial test
 3. Evaluates: Proportion of all Y1 cases where AI led to correction of an initially incorrect diagnosis

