2. STUDY OBJECTIVES

2.1 Primary Objective

To evaluate and compare the diagnostic performance of clinicians in detecting acute promyelocytic leukemia (APL) from Wright-Giemsa-stained bone marrow whole-slide images under three conditions:

- **Condition X (Unaided Review):** Clinicians review slides without AI assistance.
- **Condition Y1 (AI as Double-Check):** Clinicians provide initial diagnosis, then review AI prediction and may revise their decision. Diagnoses made before and after AI exposure were recorded.
- **Condition Y2 (AI as First Look):** Clinicians review slides with AI prediction visible from the start.

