3.6 AI System (LEAP) Implementation

The LEAP AI system generates diagnostic predictions independently for all 102 WSIs before the study session begins. During the study:

- **Condition X (Unaided):** AI predictions are not shown to the clinician
- **Condition Y1 (AI as Double-Check):** AI prediction is revealed only after the clinician submits their initial diagnosis
- **Condition Y2 (AI as First Look):** AI prediction is visible throughout the review

AI predictions are presented as binary classifications (APL vs. non-APL).

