3.7 Masking and Blinding

The study employs triple masking:

- **Patients:** Patients are blinded to the study arm to which their samples are assigned.
- **Care Provider:** Clinicians are blinded to the ground-truth diagnoses during all review sessions.
- **Investigator:** Study coordinators administering the session are blinded to the ground-truth diagnoses and to participants' arm assignments. In addition, statistical analysts are blinded to participant identities and arm assignments before results are finalized.

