5.2 Study Session Procedures

5.2.1 *Reader Orientation*

At the beginning of the study session, readers receive:

- Instructions on using the digital slide review platform
- Explanation of the three review conditions (X, Y1, Y2)
- Descriptions of the confidence rating scale (1-5)
- Opportunity to ask questions and practice with example slides not included in the study set

5.2.2 *Slide Review Process*

For each slide, readers:

1. Review the digitized WSI using the study platform with zoom and navigation capabilities
2. Formulate a diagnosis (APL vs. non-APL)
3. Assign a confidence score (1 = Random Guess; 2 = Very Doubtful; 3 = Unsure; 4 = Mostly Certain; 5 = Absolutely Certain)

4. Submit their decision (or initial decision in Condition Y1)
5. **For Condition Y1 only:** After submission, view AI prediction and optionally revise diagnosis and confidence rating
6. Proceed to the next slide

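### Section 7.3.4 measures AI benefit from the provisional pre-AI read in Condition Y1, and no planned analysis sets that read against the randomised unaided read X

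*Combined protocol and SAP*

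**What the plan says.** Section 2.1 defines the Double-Check condition: "Clinicians provide initial diagnosis, then review AI prediction and may revise their decision". Section 3.6 adds that the "AI prediction is revealed only after the clinician submits their initial diagnosis". Orientation (5.2.1) includes an "Explanation of the three review conditions (X, Y1, Y2"), and clinician masking in 3.7 goes no further than the true diagnosis: "Clinicians are blinded to the ground-truth diagnoses during all review sessions". Readers therefore know, when giving a first Y1 answer, that it is provisional and that the AI result comes next.

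The analysis in 7.3.4 stays inside Y1: "For Condition Y1 only, identify the diagnosis before (Y1_PRE) and after the AI-generated prediction is displayed (Y1_POST"). It labels changes against ground truth, the favourable class being "Beneficial (I→C): Incorrect initial diagnosis corrected after viewing AI". Test 2 is described as "Test: One-sided exact binomial test comparing number of beneficial vs. harmful changes". Test 3 is worded causally: "Null hypothesis: Improvement rate = 0 (AI provides no benefit").

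Two other places do set assisted against unassisted reading. Section 7.2.1 runs a Friedman test over X, Y1 and Y2, with pairwise Wilcoxon tests if it is significant. Section 6.2.5 defines net benefit as the accuracy gap separating the assisted from the unassisted conditions. Under 3.4, each reader's slides are split at random into three sets of 34, balanced on APL status, so X is a randomised comparator within reader.

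**The concern.** A correction in Y1 shows gain over unaided reading only if the first Y1 read is as good as the reader's unaided read would have been. Someone who knows that a second opinion is about to appear, with a chance to revise, may work less hard on the first answer. Some corrections would then only restore ordinary unaided performance. The opposite is also possible: expecting an immediate comparison with the AI may make the first read more careful, and 7.3.4 would then understate the gain.

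X is the natural check on this, and it goes unused for the purpose. What is at stake is the reading of one secondary outcome. Tests 2 and 3 could be positive while the randomised X versus Y1 contrast shows nothing, and the plan does not say which of the two supports a statement about AI benefit.

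**Working it through.** **Inputs from the documents.** 10 readers (5.3), 34 slides per reader per condition (3.4), 1,020 decisions in total (5.3). Check: 10 × 3 × 34 = 1,020, which agrees. X and Y1 each contribute 10 × 34 = 340 reads.

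**Assumed inputs.** The documents give no accuracy or change rates. Ranges used: accuracy 80% to 95%, first-read dip 1 to 5 points, harmful-change rate 0% to 2%.

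**1. Which reads are compared**

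| Section | Comparison | X against Y1_PRE? |
|---|---|---|
| 7.2.1 | X, Y1, Y2; which Y1 diagnosis is not stated | Not specified |
| 6.2.5 | Unaided against aided accuracy | Not specified |
| 7.3.1 | Time in X, Y1, Y2; which Y1 time is not stated | Not specified |
| 7.3.3 | Agreement with AI, between conditions | No; 6.2.3 uses final diagnoses |
| 7.3.4 | Y1_PRE against Y1_POST | No |
| 7.3.5.1, 7.3.5.2 | Confidence, Y1_PRE against Y1_POST | No |

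**2. What the 7.3.4 counts estimate.** The net count, (I→C minus C→I)/340, equals Y1_POST − Y1_PRE in accuracy. The gain over unaided reading is

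Y1_POST − X = (Y1_POST − Y1_PRE) + (Y1_PRE − X).

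The two agree only if the last term is zero, and no analysis is specified to estimate that term.

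**3. How little Test 2 needs.** With b beneficial and h harmful changes, the one-sided p is P(B ≥ b) for B ~ Binomial(b + h, 0.5).

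| h | Smallest b with p ≤ 0.05 | p | Net change, (b − h)/340 |
|---|---|---|---|
| 0 | 5 | 0.031 | 1.5 points |
| 1 | 7 | 0.035 | 1.8 points |
| 2 | 9 | 0.033 | 2.1 points |
| 3 | 10 | 0.046 | 2.1 points |

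Section 7.1.2 sets a two-sided 0.05, while 7.3.4 names one-sided tests. At one-sided 0.025 with no harmful changes, 6 of 6 are needed (p = 0.016; 6/340 = 1.8 points).

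**4. Test 3.** Under a null rate of 0, P(at least one correction in 340) = 0, so a single correction rejects it. Harmful changes are not netted off.

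**5. Illustration.** Suppose Y1_PRE is 82% and X is 85%. Then 0.03 × 340 = 10.2, about 10 extra initial errors. If underlying changes are 10 beneficial and 6 harmful, 10 of 16 gives p = 0.227. If the AI call also leads to correction of the 10 extra errors, 20 of 26 gives p = 0.0047. Those 10 add nothing over unaided reading.

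**6. No gain over X, first read lower by d.** Set Y1_POST accuracy equal to X, P(beneficial) = d + h and P(harmful) = h, where h is now a rate. Results are from 100,000 simulated studies of 340 independent reads.

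| Dip d | P(Test 2 p ≤ 0.05): h = 0% | h = 1% | h = 2% |
|---|---|---|---|
| 1 point | 26% | 18% | 15% |
| 2 points | 81% | 49% | 37% |
| 3 points | 98% | 76% | 62% |
| 5 points | 100% | 97% | 92% |

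**7. Precision of an X versus Y1_PRE estimate.** At 85% accuracy, SE = √(2 × 0.85 × 0.15/340) = 0.0274, so the 95% half-width is 1.96 × 0.0274 = 5.4 points. It is 6.0 points at 80% and 3.3 at 95%. Power is 9% to 19% for a 2-point dip, 35% to 70% for 5 points and 86% to 99% for 10 points; for 85% against 82% it is about 18%. All of this ignores clustering by reader and slide.

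**The case against.** A reader might infer that the plan never sets Double-Check against unaided reading. The documents do not support that. Section 7.2.1 includes the X versus Y1 pair, though only after a significant Friedman test, and 6.2.5 defines net benefit across unaided and aided conditions. Section 7.2.1 does not say which Y1 diagnosis enters, but 2.2 and 6.2.3 refer to final diagnoses in the concordance outcome, so the post-AI one is the likelier reading. The available text of 6.2.5 breaks off after a colon, so nothing here relies on what may have followed.

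A reader might also infer that first reads were careless. Nothing shows this. The initial diagnosis is formally submitted with its own confidence score, its time is recorded, and the bias could run either way. The dips, starting counts and full correction used above are assumptions.

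It is also fair to say that 2.2 lists revision patterns separately from net benefit, that condition-level performance is primary, and that pre-to-post change validly describes what the AI reveal does within this workflow. All of that stands. It does not remove the point, because Test 3 equates a zero correction rate with no AI benefit, and so claims more than revision behaviour.

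Finally, an X versus Y1_PRE comparison cannot settle a small dip. That is correct, and it is why an estimate with an interval is needed rather than a pass-or-fail test.

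**Conclusion.** The point holds for 7.3.4: its benefit results start from a provisional read that no planned analysis is specified to compare with X. The pre/post confidence tests in 7.3.5 share that baseline. The primary X versus Y1 contrast is not impugned. The direction and size of any bias are unknown. If the first read is worse than X by 2 to 3 points and the final Y1 read is no better than X, Test 2 is significant with probability 37% to 98%, assuming independent reads and harmful changes in 0% to 2% of reads. Test 3 gives no useful evidence on benefit in either case, since one correction is enough. The remedy is mainly about which result may support the benefit claim.

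**What to change.** 1. State that 7.2.1 and 6.2.5 use Y1_POST. Report Y1_POST minus X with a confidence interval whatever the Friedman result, and rest the benefit claim on it.
2. Add a reader-paired comparison of X with Y1_PRE: accuracy, sensitivity and specificity, with time and confidence as checks on effort. Give estimates with confidence intervals, and note that a non-significant difference does not show equivalence.
3. Reword 7.3.4, including the Test 3 null, so that the I→C and C→I counts describe revision within the Double-Check workflow, not benefit over unaided reading.
4. Interpret the counts alongside the X minus Y1_PRE estimate and its interval. Do not withhold them merely because Y1_PRE falls below X; with no true difference that happens about half the time by chance.
5. Label the added comparison post hoc, because the study is complete (10.2) and ran under version 1.0 without amendment (10.3).

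The cost is wording and one further paired comparison on recorded data. The downside is precision: Y1_POST minus X uses different slides, with a half-width of about 5.4 points at 85% accuracy by the formula in step 7. The within-slide count is tighter: with 10 beneficial and 6 harmful changes, SE = √(16 − 4²/340)/340 = 0.0117, a half-width of about 2.3 points. Both ignore clustering.

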4.2 Patients

4.2.1 Sample Size

The number of cases reviewed per participating clinician: 102 Wright-Giemsa-stained bone marrow aspirate WSIs from 102 patients

Distribution per condition: 34 slides for Condition X, 34 slides for Condition Y1, 34 slides for Condition Y2

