7.1.2 Level of Significance

A two-sided alpha level of 0.05 will be used for all comparisons.

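### Test 2 of the decision-change analysis is one-sided, against the plan's two-sided rule, so it cannot show both improvement and worsening as it claims

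*Combined protocol and SAP*

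**What the plan says.** Section 7.1.2 gives one rule with no exceptions: "A two-sided alpha level of 0.05 will be used for all comparisons".

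Section 7.3.4 specifies three exact binomial tests for Condition Y1, where each reader records a diagnosis before and after seeing the AI prediction. All three are one-sided, and none has an alpha of its own. For Test 2, which is restricted to changed diagnoses:

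- Null: "Null hypothesis: The likelihood of beneficial changes = The likelihood of harmful changes".
- Method: "Test: One-sided exact binomial test comparing number of beneficial vs. harmful changes".
- Purpose: "Evaluates: Whether changes tend to improve or worsen diagnostic accuracy".

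Test 2 does not say which tail is used. The section's rationale does so indirectly: "Evaluates whether (1) changes occur, (2) changes are beneficial, and (3) overall improvement is achieved".

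The other two tests do not weigh harm against benefit. Test 1: "Evaluates: Whether clinicians revise their diagnoses after viewing AI". Test 3: "Evaluates: Proportion of all Y1 cases where AI led to correction of an initially incorrect diagnosis".

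**The concern.** Test 2 conflicts with the general rule on sidedness and with its own stated purpose. A one-sided test can reject in one direction only. With the tail on benefit, a significant result can only mean improvement, and a large excess of harmful changes appears as a p-value near 1, indistinguishable in the plan's terms from no effect.

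This matters because diagnosis is binary (APL or non-APL), so every change is either beneficial or harmful. Test 2 is therefore the only planned test that compares, for the same reader and the same slide, how often the AI's output moved a diagnosis the right way and how often the wrong way. Decision revision is a named secondary objective (section 2.2). A reader of the results would expect this test to be able to find that AI exposure made diagnoses worse, and it could not. A second consequence is possible on the benefit side: if 0.05 is applied to the single tail, the error rate for a benefit claim can reach 5%, against the 2.5% per tail implied by section 7.1.2.

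**Working it through.** **Inputs from the documents.** Overall level 0.05, two-sided (7.1.2). Test 2 null: beneficial and harmful changes equally likely, so the probability that a change is beneficial is 0.5 (7.3.4). Y1 pairs: 34 slides per reader (4.2.1) × 10 readers (5.3) = 340.

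**Inputs that are assumed.** The documents give no expected number of changes, power or critical value for Test 2, so there is no figure of theirs to reproduce. Let m be the number of changes and b the number that are beneficial. I took m from 5 to 40 out of 340. The tail is taken as benefit, from the rationale in 7.3.4.

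**Formulas.** With X ~ Binomial(m, 0.5):

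- one-sided p for benefit = P(X ≥ b)
- two-sided p = 2 × the smaller of P(X ≥ b) and P(X ≤ b)

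For example, with b = 2 and m = 12: P(X ≤ 2) = (1 + 12 + 66)/4096 = 79/4096 = 0.0193, so two-sided p = 0.039. P(X ≥ 2) = 1 − 13/4096 = 0.997.

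**Results.**

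| Beneficial / harmful | m | One-sided p (benefit) | Two-sided p |
|---|---|---|---|
| 0 / 10 | 10 | 1.000 | 0.002 |
| 2 / 10 | 12 | 0.997 | 0.039 |
| 5 / 15 | 20 | 0.994 | 0.041 |
| 5 / 0 | 5 | 0.031 | 0.063 |
| 12 / 4 | 16 | 0.038 | 0.077 |
| 20 / 10 | 30 | 0.049 | 0.099 |

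In the first three rows a clear excess of harm is invisible to the one-sided test and significant two-sided. In the last three, benefit would be declared one-sided at 0.05 but not two-sided at 0.05.

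**How often the benefit side is affected.** The smallest b that reaches significance, one-sided 0.05 against two-sided 0.05:

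- different at m = 5 (5 against none attainable), m = 8 (7 against 8), m = 30 (20 against 21) and m = 40 (26 against 27);
- the same at m = 6 (6), m = 10 (9), m = 15 (12) and m = 20 (15), because the test is discrete.

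**Chance of finding harm.** Suppose the true share of beneficial changes is 0.25 (assumed). The two-sided test declares harm when the harmful count reaches its critical value, so the chance is P(H ≥ critical value) with H ~ Binomial(m, 0.75):

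- m = 10, critical value 9: 24%
- m = 20, critical value 15: 62%
- m = 40, critical value 27: 90%

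Under the one-sided benefit test the chance is zero at every m.

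**If the tail were harm instead.** The test could then not show improvement, so the stated purpose fails whichever tail is meant.

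**The case against.** Several points can fairly be made for the plan.

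- **The benefit-side inflation is conditional.** Test 2 has no alpha of its own. Judged against 0.025, its one-sided p-value would keep the benefit-side error rate of section 7.1.2, and 5 of 5 or 12 of 16 would not be declared significant. This stands. Inflation also depends on m: at many totals the cut-off does not move. But one-sided 0.025 would still not allow a finding of harm.
- **The tail is inferred.** This is true, but it does not rescue the test, since neither tail serves the stated purpose.
- **Harm is not hidden.** Section 6.2.4 classifies both kinds of change and calls for a net decision-change rate. The primary analysis in 7.2.1 is two-sided and could show lower accuracy with AI than without, including in Condition Y2. This stands as a limit on the consequences. However, the first is descriptive, and the second compares different slides between conditions; neither tests the direction of revisions.
- **The two-sided p-value has its own weakness.** The binomial test treats changes as independent, although they come from 10 readers who see the same fixed AI prediction for a given slide. This is a separate matter that affects both versions of the test, so the p-values above should be read as nominal.
- **The study is complete.** Section 10.2 reports completion and 10.3 reports no amendments, so a change now is made after data collection. That governs how the correction is labelled. It applies a rule already in the plan and makes benefit harder to claim, so it cannot favour the AI.

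**Conclusion.** The concern holds. The text of Test 2 contradicts section 7.1.2, and a one-sided test cannot deliver the two-directional conclusion that Test 2 promises. On the natural reading that the tail is benefit, net harm cannot be declared at any number of changes, even where the two-sided p-value is 0.002 (10 of 10 harmful).

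The benefit-side effect is smaller and conditional: it requires 0.05 to be applied to one tail, and it alters the decision at only some totals. All counts are illustrative.

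The point should be corrected but does not touch the primary endpoint. It is confined to Test 2. Tests 1 and 3 are also one-sided, but their null rate is exactly zero, where a two-sided version has no meaning.

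**What to change.** In section 7.3.4, Test 2, specify a two-sided exact binomial test at 0.05, with the null that the probability of a change being beneficial is 0.5. Add that the direction is always reported, and that a significant result with more harmful than beneficial changes is reported as net harm. This is equivalent to the exact McNemar test on pre- and post-AI correctness, a method the plan already uses for confidence levels in 7.3.5.2.

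Because data collection has ended, record the change as a dated correction that brings Test 2 into line with 7.1.2, and report the two-sided p-value alongside the one-sided one originally specified, each labelled.

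The cost is a short wording change and no new data. The downside is that the p-value for benefit doubles, so a result such as 5 of 5 or 20 of 30 beneficial would no longer be significant at 0.05.

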3.8 Ground Truth Determination

The reference standard diagnosis for each case is established using flow cytometry, immunohistochemical staining of trephine needle BM biopsies, cytogenetic analysis, and genomic testing.

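### Decision-change Test 2 (Section 7.3.4) pools changed reads as independent, although LEAP's fixed output gives all changes towards it on a slide the same sign; its p-value is not exact and can be too small if changes cluster on few slides

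*Combined protocol and SAP*

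**What the plan says.** Section 7.3.4 first computes the change rate as the "proportion of all Y1 cases with diagnostic revision", so the unit is the reader-slide read and all readers are pooled. Each change is then classed as beneficial (I→C) or harmful (C→I). Test 2 uses the changed reads only. Its hypothesis reads "Null hypothesis: The likelihood of beneficial changes = The likelihood of harmful changes" and its method "One-sided exact binomial test comparing number of beneficial vs. harmful changes". Among the reasons for the binomial approach the section lists "Provides exact p-values based on the binomial distribution rather than asymptotic approximations". It has no slide or reader term, no adjustment for clustering and no sensitivity analysis for it.

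The design sections fix what happens on a slide:

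- Section 3.6: "The LEAP AI system generates diagnostic predictions independently for all 102 WSIs before the study session begins". The prediction is shown as one of two labels, APL or non-APL.
- Section 5.2.2: the reader's diagnosis is one of the same two labels, and in Y1 it may be revised after the prediction is shown.
- Section 3.8: "The reference standard diagnosis for each case is established using flow cytometry" and other tests, so each case has one reference diagnosis for all readers.
- Sections 3.4 and 4.2.1: each reader has 34 of the same 102 slides in Y1, drawn separately for each reader.

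**The concern.** With two possible labels, every revision turns a correct diagnosis into an incorrect one or the reverse. A revision towards LEAP is I→C if LEAP is right on that slide and C→I if LEAP is wrong, whoever the reader is. Several readers who follow LEAP on one slide therefore contribute several outcomes with one common sign. The binomial test counts each as a fresh coin toss.

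Test 2 is the only planned test in Section 7 that sets corrections against harms within Y1. Test 1 asks only whether changes occur, and Test 3 counts only corrections. Section 7.2.1 compares X, Y1 and Y2 and plans no comparison before and after LEAP within Y1. A statement that LEAP-prompted changes are beneficial would therefore rest on this p-value.

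**Working it through.** **Inputs from the documents.** 10 readers (Section 5.3); 34 Y1 slides per reader out of 102 (Section 4.2.1); 1,020 decisions in total (Section 5.3).

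**The plan's own figure.** 10 × 102 = 1,020, as stated. The Y1 share is 10 × 34 = 340 reads. The plan states no p-value, power or expected number of changes for Test 2.

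**Overlap of readers on slides.** Mean Y1 readers per slide: 340/102 = 3.33. Each reader has a given slide in Y1 with probability 34/102 = 1/3, so the expected number of slides with at least two Y1 readers is 102 × [1 − (2/3)^10 − 10 × (1/3) × (2/3)^9] = 91. (APL strata are ignored, because the APL count is not given.)

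**Variance inflation.** Let q be the chance that a Y1 reader changes on a contested slide (an assumption). Changes per contested slide follow Bin(10, q/3). If all changes on a slide share one sign, the variance of the net count is inflated by the size-weighted mean cluster size, 1 + 9 × (q/3) = 1 + 3q. This is 1.3 at q = 0.1, 1.9 at 0.3, 2.5 at 0.5 and 3.4 at 0.8.

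**True size of Test 2 by simulation.** Under the null, LEAP is right on each contested slide with probability 1/2, and all changes go towards LEAP. Expected changes = contested slides × (10/3) × q. Nominal level: one-sided 5%. The number of contested slides and q are assumptions. Repeat runs agree to within about one percentage point.

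| Contested slides | q | Expected changes | True size |
|---|---|---|---|
| 102 | 0.05 | 17 | 3.8% |
| 102 | 0.07 | 24 | 5.0% |
| 30 | 0.10 | 10 | 4.1% |
| 20 | 0.15 | 10 | 5.0% |
| 12 | 0.25 | 10 | 6.6% |
| 40 | 0.25 × 0.7 = 0.175 | 23, on about 18 slides | 7.0% |
| 20 | 0.5 × 0.7 = 0.35 | 23, on about 14 slides | 10.1% |
| 15 | 0.6 × 0.7 = 0.42 | 21, on about 12 slides | 11.6% |
| 10 | 0.8 × 0.7 = 0.56 | 19, on about 9 slides | 12.4% |
| 8 | 0.9 × 0.7 = 0.63 | 17, on about 7 slides | 14.2% |
| 20 | 0.80 | 53 | about 16% |

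Where q is a product, it is the chance that the first read disagrees with LEAP times the chance of then switching. With independent changes in those five settings the size is 3.1-3.6%, below 5% because the binomial is discrete. The excess is due to clustering.

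**Changes away from LEAP.** These have the opposite sign. If 10% of changes go that way, the 8-slide row falls from about 14% to 10.7% and the 40-slide, q = 0.175 row to 5.7%.

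**Slide as the unit.** Under the same null, a sign-flip test on each slide's net change had size 2.0-4.3%, never above nominal.

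**Two illustrations.** Twelve changes split 10 to 2 give a binomial p of 0.019. If they lie on six slides split 5 to 1, a slide-level sign test gives (6 + 1)/64 = 0.109. Twelve beneficial changes on four slides give 0.5^12 = 0.0002 by read and 0.5^4 = 0.0625 by slide.

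**The case against.** The strongest reply is that the inflation is conditional. Nothing in the documents says that changes concentrate on a few hard slides, and the first four rows of the table show a size at or near nominal. The number of slides alone does not decide it: 10 changes on about 8 slides give 5.0%, whereas 17 on about 7 give 14.2%. This stands, and a reader might wrongly infer that the p-value is too small whatever the data.

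A reader might also infer that the signs of all changes on a slide are perfectly correlated, or that the sample size is simply the number of slides. The documents do not support either. Section 5.2.2 allows revision in both directions, and the inflation is 1 + 3q, which is modest when q is small.

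The four-slide illustration is near the worst case. It needs three of an average 3.33 Y1 readers (about 90%) to err and then switch on every one of the four slides, and no one-sided sign test on four slides can go below 0.0625.

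The target of inference matters too. If the 102 slides are taken as fixed and readers act independently, slide clustering does not inflate the error: simulated size with LEAP right on half of the contested slides was 2.3-3.0%. The plan states no such restriction, however, and the question in Section 1.3, whether LEAP improves clinicians' diagnostic performance, reaches beyond these slides.

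Finally, Test 2 is one of three tests of one secondary outcome. The primary analysis in Section 7.2.1 works on one value per reader and condition, and the change rate and I→C and C→I counts remain valid descriptions. This bears on severity. It does not rescue the claim of exactness.

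**Conclusion.** The point holds in a conditional form. For inference beyond these 102 slides, the read-level binomial p-value of Test 2 is not exact, because changes towards LEAP on a shared slide must agree in sign and the plan makes no allowance for it. Whether the p-value is materially too small depends on a pattern of changes that the documents do not give: little or no excess if changes are few or thinly spread, roughly a doubling or tripling of the nominal 5% if about 20 changes sit on about 7-14 slides, and somewhat more under heavy switching. The sponsor could not know in advance which case would apply, and a slide-level test keeps its level in all of them.

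This should be fixed, but it does not threaten the trial's main result. A reader might infer that the primary comparison of conditions is also compromised by this mechanism; it is not. The one-sided form of Test 2, against the two-sided level in Section 7.1.2, is a separate matter.

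**What to change.** In Section 7.3.4:

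1. Make the slide the unit for Test 2. For each slide, sum (I→C minus C→I) over its Y1 readers, and apply a sign-flip test to these net values over slides with at least one change.
2. Report how many distinct slides and how many distinct readers contribute changes. The sign-flip test takes only the slide as its unit, so the spread over readers should be visible.
3. Withdraw the claim of exact p-values for the read-level binomial test.

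Sections 10.2 and 10.3 record the study as complete in October 2025 with no amendments. The slide-level test should therefore be labelled a post hoc correction and reported beside the prespecified result, with any claim that changes were beneficial based on it.

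The work is a few lines of code. Section 5.2.3 already captures slide ID, reader ID and both Y1 diagnoses, so no new data are needed. The price is a less favourable p-value and lower power when few slides have changes. The test is also conservative if inference is meant for these 102 slides only.
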